## Secondary endpoints

- Difference between the corresponding MSOT values before and after exercise [Time Frame: single time point (1 day)]: Difference of the values before and after exercise for hemoglobin-associated parameters derived by transcutaneous MSOT in patients with IC
- Reperfusion profiles of hemoglobin-associated MSOT parameters (i.e. the curves of hemoglobin-associated MSOT parameters in the first ten minutes after exercise)
- Correlation of acquired MSOT parameters with the CCDS flow profiles and PSVs [Time Frame: single time point (1 day)]: hemoglobin-associated MSOT parameters (units: arbitrary units (a.u.)) derived by transcutaneous MSOT in patients with IC correlated with the flow profiles and PSVs of A. femoralis communis and A. poplitea determined by CCDS
- Correlation of acquired MSOT parameters with the ABI [Time Frame: single time point (1 day)]: hemoglobin-associated MSOT parameters (units: arbitrary units (a.u.)) derived by transcutaneous MSOT correlated with the ABI measurements
- Correlation of acquired MSOT parameters with relative (until the first occurrence of pain) and absolute walking distance (until the first stopping due to pain) determined during the 6MWT [Time Frame: single time point (1 day)]: hemoglobin-associated MSOT parameters (units: arbitrary units (a.u.)) derived by transcutaneous MSOT correlated with relative (until the first occurrence of pain) and absolute walking distance (until the first stopping due to pain)
- Correlation of acquired MSOT parameters with maximum walking distance in the 6MWT [Time Frame: single time point (1 day)]: hemoglobin-associated MSOT parameters (units: arbitrary units (a.u.)) derived by transcutaneous MSOT correlated with the maximum walking distance in the 6MWT
- Correlation of acquired MSOT parameters with the subjectively perceived maximum walking distance in everyday life [Time Frame: single time point (1 day)]: hemoglobin-associated MSOT parameters (units: arbitrary units (a.u.)) derived by transcutaneous MSOT correlated with the subjectively perceived maximum walking distance in everyday life
- Correlation of acquired MSOT parameters with the perceived PAD-specific quality of life (VASCUQOL-6 questionnaire) [Time Frame: single time point (1 day)]: hemoglobin-associated MSOT parameters (units: arbitrary units (a.u.)) derived by transcutaneous MSOT correlated with the perceived PAD-specific quality of life (VASCUQOL-6 questionnaire)

- Correlation of the acquired MSOT parameters with the TASC-classification (angiography) [Time Frame: single time point (1 day)]: hemoglobin-associated MSOT parameters (units: arbitrary units (a.u.)) derived by transcutaneous MSOT in patients with IC correlated with the TASC-classification (angiography)  
[If angiographic imaging is already available due to routine diagnostics independently from this study.]
- Subgroup analysis: Difference between the corresponding MSOT values before and after revascularization intervention [Time Frame: two time points (2 days)]: Difference of the values before and after revascularization intervention for hemoglobin-associated parameters derived by transcutaneous MSOT in patients with IC
- Subgroup analysis: Reperfusion profiles of hemoglobin-associated MSOT parameters (i.e. the curves of hemoglobin-associated MSOT parameters in the first ten minutes after exercise) after revascularization intervention
- Subgroup analysis: Correlation of acquired MSOT parameters after intervention with the CCDS flow profiles and PSVs after intervention [Time Frame: single time point (1 day)]: hemoglobin-associated MSOT parameters (units: arbitrary units (a.u.)) derived by transcutaneous MSOT in patients with IC after revascularization intervention correlated with the flow profiles and PSVs of A. femoralis communis and A. poplitea determined by CCDS after revascularization intervention
- Subgroup analysis: Correlation of acquired MSOT parameters after intervention with the ABI after intervention [Time Frame: single time point (1 day)]: hemoglobin-associated MSOT parameters (units: arbitrary units (a.u.)) derived by transcutaneous MSOT after revascularization intervention correlated with the ABI measurements after revascularization intervention
- Subgroup analysis: Correlation of acquired MSOT parameters after intervention with relative (until the first occurrence of pain) and absolute walking distance (until the first stopping due to pain) determined during the 6MWT after intervention [Time Frame: single time point (1 day)]: hemoglobin-associated MSOT parameters (units: arbitrary units (a.u.)) derived by transcutaneous MSOT after revascularization intervention correlated with relative (until the first occurrence of pain) and absolute walking distance (until the first stopping due to pain) in the 6MWT after revascularization intervention
- Subgroup analysis: Correlation of acquired MSOT parameters after intervention with maximum walking distance in the 6MWT after intervention [Time Frame: single time point (1 day)]: hemoglobin-associated MSOT parameters (units: arbitrary units (a.u.)) derived by transcutaneous MSOT after revascularization intervention correlated with the maximum walking distance in the 6MWT after revascularization intervention

## 5 Study Methods

### 5.1 General Study Design and Plan

This is a monocentric, prospective cross-sectional study which aims to compare the optoacoustic signals in calf muscle after exercise in patients with intermittent claudication (PAD in Fontaine stage II) and a healthy control group in order to define MSOT thresholds. MSOT data will be correlated with CCDS, ABI, relative and absolute walking distance, maximum walking distance in 6MWT, subjectively perceived absolute walking distance in everyday life, PAD related life quality (VASCUQOL-6) and TASC II classification in angiographic imaging (only in case angiographic imaging is available independent from this study).

Patients with intermittent claudication will be recruited during the consulting hours of the Department of Vascular Surgery, University Hospital Erlangen. Healthy volunteers will be acquired via posters in the clinic. Following detailed information about the study and after providing written consent, relevant clinical data will be collected from the electronical patient file, if available. Otherwise a thorough anamnesis interview for relevant data is performed. The CCDS, ABI and the 6MWT will be performed. Afterwards the MSOT parameters will be recorded before and after a heel raise exercise until the occurrence of claudication pain in the calf muscle. In patients, the more affected leg is examined. In healthy volunteers, also only one leg is examined. All data will be adequately pseudonymized in compliance with data protection regulations before they are used for statistical analysis. The duration of the study for participants will be max. 90 minutes. The angiographic imaging will be reviewed and analyzed (if available independently from this study) and if the interval between MSOT measurement and angiography is less than 12 months. The complete study including the validation of the data by an independent study group is expected to be finished within one year. For a subgroup analysis, some of the IC patients having been included in the study will be reexamined after revascularization intervention.

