5.1 Primary/secondary objectives and hypotheses

Primary hypothesis:

- The quantitative MSOT value for oxygenated hemoglobin in the calf muscle of PAD patients in the claudication stage before and after active exercise until the onset of claudication pain is suitable for distinguishing a diseased from a healthy collective.

Secondary hypotheses:

- The MSOT reperfusion profiles (i.e. the curves of hemoglobin-associated MSOT parameters in the first ten minutes after exercise) of PAD patients in the claudication stage show certain patterns and differ significantly from the reperfusion profiles of healthy subjects.
- The collected MSOT parameters and their reperfusion profiles correlate with the perfusion parameters from the CCDS.
- The collected MSOT parameters and their reperfusion profiles correlate with the ABI.
- The recorded MSOT parameters and their reperfusion profiles correlate with the relative (until the first occurrence of pain) and absolute walking distance (until the first stopping due to pain) of the patient.
- The recorded MSOT parameters and their reperfusion profiles correlate with the total distance reached in the 6-minute walk test.
- The recorded MSOT parameters and their reperfusion profiles correlate with the subjectively perceived maximum walking distance achieved in everyday life.
- The recorded MSOT parameters and their reperfusion profiles correlate with the perceived PAD-specific quality of life (VASCUQOL-6 questionnaire).
- The collected MSOT parameters and their reperfusion profiles correlate with the angiographic severity of the PAD disease.

[If angiographic imaging is already available due to routine diagnostics independently from this study.]

- Subgroup analysis: The MSOT parameters measured again after revascularization intervention show characteristic changes compared to the measurements before intervention
- Subgroup analysis: The MSOT parameters measured again after revascularization intervention show tendencies towards the MSOT parameters of healthy subjects compared to the measurements before intervention
- Subgroup analysis: The reperfusion profiles of MSOT parameters measured again after revascularization intervention show characteristic changes compared to the measurements before intervention

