**Inclusion Criteria**

- Patients with manifest PAD in stage II according to Fontaine or categories 1-3 according to Rutherford or healthy volunteers
- Adults (>18 years) who are able to give their consent

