**Exclusion Criteria**

- Patients with PAD stage I, III and IV according to Fontaine or categories 0, 4, 5 and 6 according to Rutherford or healthy volunteers with diabetes mellitus, chronic renal failure, claudication symptoms, abnormal ABI or non-palpable foot pulses
- Underage persons
- Lack of written consent
- Safety concerns of the study physician (person with physical, mental or psychiatric conditions which, by the judgement of the study physician, would compromise the person's safety or the quality of the data, thereby rendering the person an ineligible candidate for the study)

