**5.4 Study Variables**

	Visit	Annotations
Index test (MSOT) 	X	Before and after exercise
Angiography 		Considered only if angiographic imaging already available in the electronic patient file due to routine diagnostics independently from this study and if less than 12 months to the date of index test; Evaluated by two independent examiners
CCDS 	X	Whether a flow-relevant stenosis is present in the examined vessels is decided by an independent reader
ABI 	X	
Clinical scores 	X	

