## Type-C:

- *multiple stenoses or occlusions with a total ≥ 15 cm vessel involvement, with or without severe calcification*
- *Recurrent stenoses or occlusions requiring treatment after two endovascular interventions*

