## 8.4 Baseline Variables

- Age
- Gender
- Affected leg/examined leg
- Risk factors for PAD (smoking, arterial hypertension, lipid abnormalities, diabetes mellitus, obesity, positive family history)
- Relevant underlying diseases (CHD, CHF, atrial fibrillation, CKD, carotid artery stenosis, previous cerebrovascular event)
- Previous surgery or interventions on the arterial vessels of the lower extremity
- Current medication
- Date of last angiography

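### The SAP accepts angiograms within 12 months of MSOT without requiring that the examined leg was untreated in between, so some TASC classes in a secondary analysis may be outdated

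*SAP*

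**What the plan says.** Angiography is not a study procedure. The protocol (5.1) makes its use conditional: "If angiographic imaging is already available due to routine diagnostics independently from this study". The protocol gives no time window. The SAP adds one, in 5.1 ("if the interval between MSOT measurement and angiography is less than 12 months") and in the table of study variables in 5.4 ("if less than 12 months to the date of index test"). SAP 5.4 also requires that the image is in the patient file from routine care and is evaluated by two independent examiners.

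Patients qualify by clinical stage: "Patients with manifest PAD in stage II according to Fontaine or categories 1-3 according to Rutherford or healthy volunteers". The stage-related exclusion concerns other stages only ("Patients with PAD stage I, III and IV according to Fontaine or categories 0, 4, 5 and 6 according to Rutherford"), and no remaining exclusion mentions earlier revascularization. Earlier treatment is in fact expected. SAP 8.4 lists "Previous surgery or interventions on the arterial vessels of the lower extremity" among the baseline variables, and one criterion for femoro-popliteal TASC type C in SAP 5.4 is "Recurrent stenoses or occlusions requiring treatment after two endovascular interventions". SAP 8.4 also records "Date of last angiography", but no rule combines that date with the date of an intervention.

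**The concern.** A time limit on imaging is meant to ensure that the image shows the leg as it was when MSOT was measured. Elapsed time is a weak guide to that when the leg may have been treated in the interval, because a revascularization changes the anatomy at once. An image taken before such a treatment passes the rule as written, although the lesion it shows may have been opened or bypassed.

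Recruitment takes place in vascular surgery consultation hours (Protocol 8.3), so previously treated legs are plausible. Careful reading does not help: blinding (SAP 5.3) and double reading (SAP 5.4) protect against misreading an image, not against a correctly read image that is out of date.

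At stake are the secondary endpoint correlating MSOT parameters with TASC class (SAP 4.3), the subpopulations defined partly by TASC (SAP 7.3), and the tables by combined TASC group, including sensitivity and specificity (SAP 12.6). ABI and CCDS are measured at the study visit, so angiography is the comparator most exposed to this mismatch.

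**Working it through.** The plan states no figure for this point, so there is none to reproduce. The check has two parts.

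**1. Does any rule close the gap?**

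- SAP 5.1 and 5.4 limit the interval only. They name no direction and set no condition on treatment in between. The protocol's requirement that imaging already exist suggests an image that predates the visit, but neither document says so.
- The eligibility criteria (Protocol 8.1, SAP 5.2) do not exclude previous revascularization.
- SAP 7.3 allows CCDS, where necessary, to confirm a flow-relevant stenosis. It does not say that CCDS overrides or removes a TASC class.
- SAP 7.4 (missing data) and 8.2 (deviations) do not cover an outdated class, which is neither missing nor a deviation.
- SAP 8.4 collects earlier interventions and the date of the last angiography. It does not explicitly list the date or side of the intervention.

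The gap is therefore open. The main route is this: angiogram, then treatment of the examined leg or its inflow, then persistent or recurrent claudication, then the first MSOT visit, all within 12 months and with no newer image used.

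**2. How much could it matter?** All inputs here are assumptions: a Spearman correlation of 0.46 in absolute value (what a latent correlation of 0.5 gives with four equally frequent classes) and an outdated share *f* of 10%, 20% or 30%.

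If outdated classes are random draws from the same class distribution, unrelated to the current state of the leg, the expected correlation is (1 − *f*) × 0.46:

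| *f* | Calculation | Result |
|---|---|---|
| 10% | 0.90 × 0.46 | 0.41 |
| 20% | 0.80 × 0.46 | 0.37 |
| 30% | 0.70 × 0.46 | 0.32 |

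A simulation of this model gave 0.414, 0.369 and 0.323, starting from 0.458.

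If instead more severe legs are treated preferentially and their perfusion improves, the simulated values are 0.39, 0.31 and 0.24. With a latent correlation of 0.3, the starting value is 0.27, and at 30% it falls to 0.19 (random) or 0.14 (severe legs first). Every scenario moves towards zero.

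**Set against sampling error.** At the planned maximum there are 2 × 31 = 62 patients, and fewer will have angiography. With Fisher's transformation, atanh(0.46) = 0.497 and the standard error is 1/√59 = 0.130. The 95% limits are 0.497 ± 0.255, which back-transform to 0.24 and 0.64. The three values in the table lie inside that interval.

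Power for the correlation (two-sided 0.05, variance 1.06/(n − 3)) would fall from about 0.96 to 0.83 with 62 angiograms if the coefficient dropped from 0.46 to 0.37. With an assumed 40 angiograms it would fall from about 0.84 to 0.63.

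**The case against.** The strongest reply is that the route is narrow and the consequences are small. Much of that stands.

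- A reader might infer that the re-examined subgroup pairs a pre-treatment TASC class with post-treatment MSOT values. The listed endpoints do not support this. Treatment of study patients follows the first visit (Protocol 9.2), and the post-intervention correlations in SAP 4.3 are with CCDS, ABI and walking distances, not TASC. Only the general objective of re-recording all parameters (SAP 4.2) leaves some ambiguity.
- A reader might infer that the diagnostic thresholds are compromised. They are not: the Youden cutpoint in SAP 9.2 compares healthy volunteers with claudication patients and does not use TASC.
- A reader might say that age is the only condition on the image. It is not: the image must also come from routine care, independently of the study.
- Recording the last angiography points towards the most recent image, although the SAP does not say that this is the image classified.
- The aTASC grouping is less sensitive than the illustration suggests. aTASC 2 covers every femoro-popliteal grade when the aorto-iliac level is normal or A/B, so a femoro-popliteal treatment that leaves a residual TASC lesion does not change the group.
- A treated leg's former class need not be unrelated to its current state, so the random-class model may overstate the loss.

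What remains is that the rule, followed as written, admits outdated classes, and nothing elsewhere in either document removes them.

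**Conclusion.** The gap is real but minor. It concerns patients whose examined leg or inflow was treated between angiogram and MSOT. It affects one secondary correlation and the TASC/aTASC analyses, and leaves the primary analysis alone. The likely effect is a weaker MSOT–TASC association, so MSOT would look worse than it is; none of the scenarios examined makes it look better.

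The size cannot be determined from the documents. The figures above show how the loss depends on assumed inputs and are not estimates for this study. This is a cheap improvement, not a flaw that threatens the conclusions. Its main value is that the rule would be fixed before the data are seen, which avoids case-by-case exclusions once MSOT values are known.

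**What to change.** Add to SAP 5.1 and 5.4 that a TASC/aTASC class is used only if the angiogram lies within 12 months of MSOT and no revascularization of the examined leg or its inflow took place between the two dates, in whichever order. Otherwise the class is missing for that analysis, and SAP 7.4 already excludes the subject from the specific sub-analysis.

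Add the date and side of earlier arterial interventions to SAP 8.4, taken from the patient file. Report the interval between angiogram and MSOT, its direction, and the number of classes set to missing.

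Reclassifying on a final post-treatment image is not a safe general substitute: aTASC needs the aorto-iliac, femoro-popliteal and infrapopliteal levels, and the documents do not say that such an image covers all three.

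The cost is one sentence, two data items, and a few angiograms lost from a secondary analysis.

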### 5.2 Study Population

Statistical analysis of the data of the previous study (MSOT\_PAD, NCT04641091) suggests a necessary number of approximately 100 participants in total (minimum 48 participants, maximum 124 participants). This is planning with similar group sizes for IC patients and healthy volunteers. Age should be similar in the investigated groups.

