8.1 Inclusion and exclusion criteria

Statistical analysis of the data of the previous study (MSOT_PAD, NCT04641091) suggests a necessary number of approximately 100 participants in total (minimum 48 participants, maximum 124 participants, see below). This is planning with similar group sizes for IC patients and healthy volunteers. Age should be similar in the investigated groups.

Definition of patient groups:

- PAD IIa
- PAD IIb

Definition of healthy control group:

- no PAD previously known

- no diabetes mellitus previously known
- no chronic renal insufficiency previously known
- no symptoms of intermittent claudication
- ABI with values between 0.9 and 1.4 (screening examination before inclusion in the study)
- palpable foot pulses

Inclusion Criteria

- Patients with manifest PAD in stage II according to Fontaine or categories 1-3 according to Rutherford or healthy volunteers
- Adults (>18 years) who are able to give their consent

Exclusion Criteria

- Patients with PAD stage I, III and IV according to Fontaine or categories 0, 4, 5 and 6 according to Rutherford or healthy volunteers with diabetes mellitus, chronic renal failure, claudication symptoms, abnormal ABI or non-palpable foot pulses
- Underage persons
- Lack of written consent
- Safety concerns of the study physician (person with physical, mental or psychiatric conditions which, by the judgement of the study physician, would compromise the person's safety or the quality of the data, thereby rendering the person an ineligible candidate for the study)

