8.2 Expected sample size

Statistical sample size calculation based on the results of the previous study (MSOT_PAD, NCT04641091) suggests a necessary study collective of at least 48 to a maximum of 124 subjects/patients. The two-sample t-test power calculation with a power of 0.8 gave an n of about 12 for each group (study group 1 - healthy volunteers, study group 1 - claudication patients, study group 2 - healthy volunteers, study group 2 - claudication patients). Additional sample size planning based on the AUC, which should be at least 0.7 for a relevant significance, gave an n of 31 subjects/patients for each group (with a significance level of 0.05 and a power of 0.8).

These calculations were based on data comparing healthy subjects with patients in stage IIb who, however, had not been adequately exercised (all only with the same walking distance of 150 meters). Due to the hypothesis of the study that the ability to differentiate between healthy subjects and claudication patients can be increased by adequate provocation testing, the sample size estimated here on the basis of the previous data is to be regarded as conservative. For this reason, after the inclusion of the first 25 patients and the first 25 healthy test persons, the necessary total

sample size will be reevaluated in cooperation with the Institute for Biometry – on the basis of the data collected up to that point.

Dropout is not considered because the study is performed during a single visit.

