## 6 Determination of Sample Size

Statistical sample size calculation based on the results of the previous study (MSOT\_PAD, NCT04641091) suggests a necessary study collective of at least 48 to a maximum of 124 subjects/patients. The two-sample t-test power calculation with a power of 0.8 gave an n of about 12 for each group (study group 1 - healthy volunteers, study group 1 - claudication patients, study group 2 - healthy volunteers, study group 2 - claudication patients). Additional sample size planning based on the AUC, which should be at least 0.7 for a relevant significance, gave an n of 31 subjects/patients for each group (with a significance level of 0.05 and a power of 0.8).

These calculations were based on data comparing healthy subjects with patients in stage IIb who, however, had not been adequately exercised (all only with the same walking distance of 150 meters). Due to the hypothesis of the study that the ability to differentiate between healthy subjects and claudication patients can be increased by adequate provocation testing, the sample size estimated here on the basis of the previous data is to be regarded as conservative. For this reason, after the inclusion of the first 25 patients and the first 25 healthy test persons, the necessary total sample size will be reevaluated in cooperation with the Institute for Biometry – on the basis of the data collected up to that point.

Dropout is not considered because the study is performed during a single visit.

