## 7 General Considerations

### 7.1 Timing of Analysis

The final analysis will be performed after the last patient entered the study. Study collectives for study group 1 (derivation of thresholds) and study group 2 (validation of thresholds) will be handled separately.

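### The stated need for about 100 participants follows from neither printed calculation (48 or 124); split evenly, 100 gives about 0.70 to 0.72 power at the plan's AUC of 0.7

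*SAP*

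**What the plan says.** SAP 5.2 states that analysis of the previous study "suggests a necessary number of approximately 100 participants in total (minimum 48 participants, maximum 124 participants"; Protocol 8.1 gives the same figure and points to the text further down. Both plan similar numbers of patients and healthy volunteers.

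The derivation is in Protocol 8.2 and, in the same terms, SAP 6. There are two calculations. The first reads: "The two-sample t-test power calculation with a power of 0.8 gave an n of about 12 for each group". The groups are the four cells formed by study group (1 or 2) and status (healthy or claudication). The second is based on the AUC, "which should be at least 0.7 for a relevant significance, gave an n of 31 subjects/patients for each group", with significance level 0.05 and power 0.8.

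On the source of these figures, SAP 6 says: "These calculations were based on data comparing healthy subjects with patients in stage IIb who, however, had not been adequately exercised". Because the new exercise is expected to improve differentiation, "the sample size estimated here on the basis of the previous data is to be regarded as conservative". The total is to be re-evaluated after the first 25 patients and 25 healthy participants, "on the basis of the data collected up to that point".

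SAP 7.1 adds: "Study collectives for study group 1 (derivation of thresholds) and study group 2 (validation of thresholds) will be handled separately". SAP 9.2 plans sensitivity and specificity at the Youden cutpoint, with 95% confidence intervals. It does not plan an estimate of the AUC.

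**The concern.** A figure described as necessary should trace back to a calculation. This one does not: Protocol 8.1 points the reader further down, and the text there yields only 48 and 124. The two ends also rest on different effects, so the range does not surround a single target, and a number between them has no defined power until a target is named.

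What is at stake is how the design is read. The only target the plan prints is an AUC of at least 0.7. Someone who takes about 100 as the working size cannot tell from the text what chance each study group has of detecting that AUC. The conservative label suggests there is margin in hand, but it counts only the hoped-for gain from the heel-raise exercise. It leaves out that the planning data were healthy versus stage IIb, while SAP 5.2 also enrols stage IIa.

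**Working it through.** **Inputs.** About 12 and 31 per cell, power 0.8, significance level 0.05 (stated with the AUC calculation) and AUC 0.7 come from SAP 6 and Protocol 8.2. The total of 100 comes from SAP 5.2 and Protocol 8.1. Separate treatment of the two study groups comes from SAP 7.1. The Wilcoxon test comes from the statistical methodology in Protocol 11. Assumptions: null AUC 0.5, two-sided testing, equal-variance normal data, and an even split of 100 over four cells.

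**1. Totals.** 4 × 12 = 48 and 4 × 31 = 124, as stated. 100 / 4 = 25 per cell, which is the result of neither calculation.

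**2. Reproducing the 31.** The binormal (Obuchowski) variance for one group of size n with equal allocation is V(A)/n, where V(A) = 0.0099 · exp(−a²/2) · [(5a² + 8) + (a² + 8)] and a = 1.414 · Φ⁻¹(A).

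- A = 0.5: a = 0, V = 0.0099 × 16 = 0.1584, √V = 0.398.
- A = 0.7: a = 0.7415, a² = 0.550, V = 0.0099 × 0.760 × 19.30 = 0.1452, √V = 0.381.
- n = [(1.96 × 0.398 + 0.8416 × 0.381) / 0.2]² = (1.1007 / 0.2)² = 30.3, so 31.

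The plan's figure reproduces two-sided. One-sided, the same formula gives 23.8, so 24, which does not match.

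**3. Power at 25 per cell for AUC 0.7.** By the same formula, (0.2 − 1.96 × 0.398/5) / (0.381/5) = 0.0440 / 0.0762 = 0.577, and Φ(0.577) = 0.72. Simulating the Wilcoxon rank-sum test on normal data separated by d = √2 · Φ⁻¹(0.7) = 0.742 gives the middle column below.

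| Per cell | Total | Wilcoxon (simulated) | Obuchowski |
|---|---|---|---|
| 31 | 124 | 0.80 | 0.81 |
| 25 | 100 | 0.70–0.71 | 0.72 |

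Other formulas that return 31 within rounding tolerance put power at 25 per cell between 0.69 and 0.75.

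**4. AUC needed for 0.8 power at 25 per cell.** About 0.72 by either method (Wilcoxon 0.722; Obuchowski power 0.802 at AUC 0.72).

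**5. Effect behind the 48.** The t-test inputs are not printed. With 12 per group, power 0.8 and two-sided 0.05, the detectable effect is d = 1.197, which corresponds to AUC = Φ(1.197/√2) = 0.80. At that effect, 25 per cell gives Wilcoxon power of about 0.98.

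**6. The conservative label.** Two influences pull in opposite directions. The Figure 1 legend in Protocol 4 says that the HbO₂ signal falls with increasing stage, so adding IIa patients may narrow the contrast with healthy volunteers. Yet SAP 5.4 defines IIa by a pain-free distance above 200 m, so the earlier 150 m walk lay below their pain threshold, and exercise to pain may act strongly in them. The documents give no IIa figures, so the net direction cannot be computed.

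**The case against.** The strongest reply is that the documents never claim 0.8 power for 100. They attach it to 12 and 31 per group, call 100 approximate and print the whole range beside it. That stands: a reader might infer that 100 carries 0.8 power, but the text does not say so. What remains is that 100 is called necessary without a calculation or a stated power.

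Other readings go further than the documents allow:

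- **No split between study groups exists.** The split is not in the text, but Protocol Figure 2 (study design and flow) is not shown and may give it. The 25 per cell is therefore an assumption.
- **The 0.8 behind the 48 is wrong.** At 12 per cell, power for AUC 0.7 is only about 0.38 to 0.41. But the 48 was sized on a different and larger effect, and two planning effects are not in themselves an error.
- **Choosing 100 makes significance too easy to reach.** At 25 per cell an observed AUC of about 0.66 is already significant. At 31 per cell the threshold is lower still, about 0.645, so this is not a consequence of choosing 100.
- **One-sided testing explains the 100.** It would give about 0.80 to 0.82 at 25 per cell, but the documents do not say one-sided, and it does not reproduce their 31.
- **Pooling restores the power.** Comparing 50 with 50 would give about 0.95, but SAP 7.1 keeps the study groups apart.

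The re-evaluation at 25 + 25 uses data from the enrolled population under the new exercise and can change the total. That is real, though partial, mitigation: the text gives it no target or rule. The conservative label is also openly tied to the study hypothesis, so what is left there is a matter of wording.

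**Conclusion.** The point holds, and it is minor. The figure of about 100 is not derived from either printed calculation. Under an even split, two-sided 0.05, a null AUC of 0.5 and separate study groups, its power at AUC 0.7 is about 0.70 to 0.72, below the 0.8 used in both calculations. The shortfall is specific to that target: it disappears from an AUC of about 0.72, and power is about 0.98 at the effect implied by the t-test. The conservative claim is not shown, because it rests on the hypothesis under test and on IIb data alone.

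A reader might conclude that the study is too small. The documents do not support that, since the effect of the new exercise in the enrolled IIa/IIb mix is unknown in direction and size. No planned test or estimate becomes invalid.

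**What to change.** (a) **Protocol 8.1 and SAP 5.2.** Name the target behind the total and restate its power. For example: *for AUC 0.7 versus 0.5, two-sided 0.05, 31 per cell (124 in total) gives power of about 0.80 and 25 per cell (100 in total) about 0.70 to 0.72; the minimum of 48 rests on the larger effect used in the t-test calculation.* Whether to plan for 124 or accept about 0.70 at 100 stays the sponsor's choice.

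(b) **Protocol 8.2 and SAP 6.** Replace the conservative claim with a statement that the new exercise may raise the difference and the inclusion of stage IIa may lower it, with the net effect unknown. Keep the 25 + 25 re-evaluation based on the data collected in the enrolled IIa/IIb mix. Tying it to a fixed AUC of 0.7 would return about 31 per cell whatever those data showed.

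(c) **SAP 9.2.** Report the AUC with a 95% confidence interval (for example DeLong) in each study group, beside sensitivity and specificity, since the AUC is the stated sizing target. At 25 per cell the half-width to expect is about 0.15 at AUC 0.70 and 0.12 at AUC 0.80.

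The cost is wording in four sections and one added estimate per study group from data already planned. The correction itself requires no extra participants.
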